Visit 2 (60 [±14] days after Visit 1): Collection of Safety Information and Vaccination

- 1) If the DC1 information from Day 0–7 has not yet been obtained, obtain it at this time by interviewing the parents. Review the pages of the DC1 with the parent / guardian, including any AEs, medications, or therapy that occurred since vaccination.
- 2) Check medications and record reportable ongoing medications.
- 3) Conduct a physical examination, including, but not limited to, examination of the head (ear, nose, and throat), neck, heart, lungs, abdomen, and extremities. If a routine examination had been performed within the past week by a qualified health care provider, it does not need to be repeated unless there were changes in health status, in which case it may be limited to the affected area.
- 4) Take the subject's temperature. If the temperature is $\geq 38.0^{\circ}\text{C}$ / $\geq 100.4^{\circ}\text{F}$, postpone vaccination until the condition is resolved.
- 5) Contact IRT system for vaccine allocation.
- 6) Inject the following study vaccines. Each vaccine should be administered in an assigned location (see Operating Guidelines) and documented appropriately. Refer to [Table 5.3](#) for details on vaccinations and route of administration at V01, V02, and V03.

When multiple vaccines are administered at a single visit, each vaccine should be administered at a different anatomic site. If vaccines are given in the same limb, the injection sites should be separated by 1 inch / 2.5 cm or more, so that any local reactions can be differentiated ([40](#)).

Pentacel and ENGERIX-B (as applicable) should be given in the same thigh. They should not be administered in the same thigh as SP0202 or Prevnar. For details see Operating Guidelines.

Failure to administer vaccines in the designated limb will not constitute a protocol deviation, but should be recorded as a comment in the vaccination form of the eCRF. If the vaccines are not administered in the recommended limb(s), this should be corrected for subsequent injections.

- 7) Keep the subject under observation for 30 minutes and record any adverse reaction in the source document.
- 8) Give the parent / guardian a DC2. Remind parents to carefully report any clinical signs / diagnosis experienced at the same time as the fever episode $> 39.5^{\circ}\text{C} / 103.1^{\circ}\text{F}$.

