5.2.7 Contraindications for Subsequent Vaccinations

5.2.7.1 Temporary Contraindications

Toddlers

Not applicable.

Infants

Should an infant experiences one of the conditions listed below, the Investigator will postpone further vaccination until the condition is resolved. Postponement must still be within the timeframe for vaccination indicated in the Table of Study Procedures.

- 1) Febrile illness (temperature $\geq 38.0^{\circ}\text{C}$ [$\geq 100.4^{\circ}\text{F}$]) or moderate or severe acute illness / infection on the day of vaccination, according to Investigator judgment
- 2) Receipt of any vaccine (other than the study vaccine[s]) in the 4 weeks preceding the study vaccination or planned receipt of any vaccine from enrollment through the last study Visit in

which SP0202 or Prevnar 13 is injected (V05), except for influenza vaccination or COVID-19 vaccination, which may be received at least 2 weeks before or 2 weeks after any study vaccination. This exception includes monovalent pandemic influenza vaccines and multivalent influenza vaccines, and COVID-19 vaccines, as applicable per local recommendation.

- 3) Long-term systemic corticosteroid therapy (prednisone or equivalent for more than 2 consecutive weeks within the past 3 months preceding the study vaccination)

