5.2.7.2 Definitive Contraindications

Toddlers

Not applicable.

Infants

Should a subject experience 1 of the conditions listed below, the Investigator will discontinue vaccination:

- 1) An anaphylactic or other significant allergic reaction to the previous dose of vaccine
- 2) Receipt of immunosuppressive therapy, such as anti-cancer chemotherapy or radiation therapy
- 3) Ongoing clinical AE related to the previous study vaccination, and in the Investigator's opinion, contraindicating further vaccination
- 4) SAE related to the study vaccine following the previous study vaccination

Subjects with a definitive contraindication will continue to be followed up for the study-defined safety and immunogenicity assessments, as applicable.

In the event of a local or national immunization program with a pandemic influenza vaccine or a COVID-19 vaccine, subjects who receive pandemic influenza vaccine or COVID-19 vaccine at any time during the study will not be withdrawn from the study.

The following AEs constitute absolute contraindications to subsequent vaccinations, according to their respective Product Information. If a subject should experience any of these events during the study, irrespective of causality, that subject is not to receive any additional study vaccines but should continue in the study and be followed up for safety only, as per protocol. Only the vaccine which has a related SAE or a definite contraindication will be stopped wherever it is possible to identify the vaccine that caused the event.

Prevnar

- 1) Hypersensitivity to the active substances, to any of the excipients, to diphtheria toxoid, or to a previous dose of Prevnar 13

Pentacel

- 1) Severe allergic reaction (eg, anaphylaxis) after a previous dose of Pentacel, any ingredient of Pentacel, or any other diphtheria toxoid, tetanus toxoid, pertussis-containing vaccine, inactivated poliovirus vaccine or *H. influenzae* type b vaccine
- 2) Encephalopathy within 7 days of a previous pertussis-containing vaccine with no other identifiable cause
- 3) Progressive neurologic disorder including infantile spasms, uncontrolled epilepsy, or progressive encephalopathy until a treatment regimen has been established and the condition has stabilized

ENGERIX-B

- 1) Severe allergic reaction (eg, anaphylaxis) a previous dose of any hepatitis B-containing vaccine, or to any component of ENGERIX-B, including yeast

RotaTeq

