- 1) Demonstrated history of hypersensitivity to the rotavirus vaccine or any component of the vaccine
- 2) History of Severe Combined Immunodeficiency Disease (SCID)
- 3) Episode of intussusception

M-M-R_{II}

- 1) Hypersensitivity to any component of the vaccine, including gelatin
- 2) Anaphylactic or anaphylactoid reactions to neomycin
- 3) Febrile respiratory illness or other active febrile infection
- 4) Patients receiving immunosuppressive therapy. This contraindication does not apply to patients who are receiving corticosteroids as replacement therapy, eg, for Addison's disease
- 5) Individuals with blood dyscrasias, leukemia, lymphomas of any type, or other malignant neoplasms affecting the bone marrow or lymphatic systems
- 6) Primary and acquired immunodeficiency states, including patients who are immunosuppressed in association with acquired immune deficiency syndrome (AIDS) or other clinical manifestations of infection with human immunodeficiency viruses; cellular immune deficiencies; and hypogammaglobulinemic and dysgammaglobulinemic states
- 7) Individuals with a family history of congenital or hereditary immunodeficiency, until the immune competence of the potential vaccine recipient is demonstrated

VARIVAX

- 1) History of severe allergic reaction to any component of the vaccine (including neomycin and gelatin) or to a previous dose of varicella vaccine
- 2) History of primary or acquired immunodeficiency states, leukemia, lymphoma or other malignant neoplasms affecting the bone marrow or lymphatic system, AIDS, or other clinical manifestations of infection with HIV

- 3) Individuals receiving immunosuppressive therapy, including individuals receiving immunosuppressive doses of corticosteroids
- 4) Any febrile illness or active infection, including untreated tuberculosis

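### Protocol 5.2.7.2 makes febrile illness and active infection definitive contraindications to M-M-R II and VARIVAX, while 5.2.7.1 and Visit 5 only postpone; it also gives two follow-up rules for conditions in both of its lists

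*Protocol*

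**What the plan says.** **Stop.** Protocol 5.2.7.2 has a general list of four reasons to discontinue vaccination, followed by lists for each product. The product lists are introduced as absolute contraindications taken from the product information. They apply "If a subject should experience any of these events during the study, irrespective of causality", and the stated consequence is no additional study vaccines. A following sentence narrows this to the vaccine concerned where the causative vaccine can be identified. M-M-R II item 3 is "Febrile respiratory illness or other active febrile infection". VARIVAX item 4 is "Any febrile illness or active infection, including untreated tuberculosis".

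**Postpone.** Protocol 5.2.7.1 says that for its listed conditions "the Investigator will postpone further vaccination until the condition is resolved", within the visit timeframe. Its item 1 covers febrile illness (38.0°C or more) or "moderate or severe acute illness / infection on the day of vaccination, according to Investigator judgment". In Protocol 5.1.4, infant Visit 2 step 4, Visit 3 step 4 and Visit 5 step 5 each say, for a temperature of 38.0°C or more, to "postpone vaccination until the condition is resolved".

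**Follow-up.** After the general list, 5.2.7.2 keeps the infant in safety and immunogenicity assessments as applicable. For the product lists it prescribes follow-up for safety alone.

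**The concern.** M-M-R II and VARIVAX are given only at V05 (Protocol Table 5.2). The section that governs permanent stopping and the step that governs that visit should agree on what to do with a febrile child, and they do not. At stake is whether an infant receives routine measles, mumps, rubella and varicella vaccination within the study.

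The follow-up rules raise a second, separate problem. If a condition stands in both lists, both rules apply to the same infant, and the site must guess whether to take the later blood samples. Those samples decide membership of the immunogenicity analysis sets.

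**Working it through.** The plan states no figure on this point, so the check is mainly a comparison of instructions.

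**1. Infant with a febrile respiratory infection at V05.**
- Protocol 5.1.4, Visit 5 step 5: postpone.
- Protocol 5.2.7.1 item 1: postpone.
- Protocol 5.2.7.2, M-M-R II item 3 and VARIVAX item 4: contraindicated under a definitive heading, with the vaccine stopped.

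The conflict does not depend on reading the items as a lifelong bar. Even if they apply only while the illness is present, it is present here, and stopping a vaccine is a different instruction from delaying it.

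**2. Doses at risk for one such infant** (from Table 5.2, one dose of each vaccine, both at V05).
- Both items met (febrile infection): 1 + 1 = 2.
- Only VARIVAX item 4 met (for example an active infection without fever): 1.
- Postponement rule, visit kept within its window: 0. The window is fairly wide, since V05 may take place from 12 through 15 months of age.

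**3. Mild infection without fever at V05.** Visit 5 step 5 is not triggered, because it turns on temperature. Nor is 5.2.7.1 item 1, because the infection is neither febrile nor moderate or severe. VARIVAX item 4 is triggered, because it covers any active infection. One section allows VARIVAX and the other bars it.

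**4. Conditions in both lists of 5.2.7.2.**

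| Condition | General list (safety and immunogenicity) | Product lists (safety alone) |
|---|---|---|
| Immunosuppressive therapy | item 2 | M-M-R II item 4; VARIVAX item 3 |
| Severe allergic reaction to a previous dose | item 1 | for example Pentacel item 1, ENGERIX-B item 1 |

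**5. Analysis sets for an event before V04.** FAS2 needs at least one primary-series dose and a valid post-primary blood result (Protocol 12.2.1; SAP 5.2.2). With the V04 sample the infant is in FAS2; without it the infant is out. PPAS2 is usually lost either way: an infant stopped before V03 has not completed the schedule, and immune-suppressors are category 2 medication, itself a ground for exclusion (Protocol 6.7 and 12.2.3; SAP 5.2.1). An exception is a severe allergic reaction to the third dose, where the schedule is complete and PPAS2 also turns on the sample. FAS3 needs a booster dose. Taking study vaccine there to mean the PCV, an infant whose PCV has stopped before V05 is outside FAS3 under either rule.

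**6. Scale.** The plan expects 175 × (1 − 0.20) = 140 evaluable infants per group at PD3 (Protocol 12.5). One infant is 1/140 = 0.7% of that. Interval width on the log scale varies as 1/√n, so losing one infant widens it by a factor of √(140/139) = 1.0036, about 0.4%.

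**The case against.** The strongest reply is that no sensible site would be misled. The word active limits the infection items by itself, the lists are taken from product labelling, and the postponement rule appears at the visit where these vaccines are given. Fever of 38.0°C or more is also a solicited reaction recorded after every dose (Protocol Table 9.2), so treating any fever during the study as a permanent bar would turn an expected reaction into a reason to withhold later vaccines. This stands against two stronger readings that a reader might infer.

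- **A resolved fever bars the vaccines for good.** The items carry no explicit limit, whereas Pentacel item 3 has "until a treatment regimen has been established and the condition has stabilized" and M-M-R II item 7 has "until the immune competence of the potential vaccine recipient is demonstrated". That contrast is weak. Those two items describe a progressive disorder and a family history, which need such a clause because they do not simply pass.
- **All remaining vaccines, PCV included, are lost.** A site would have to overlook 5.2.7.1, the visit steps and the sentence narrowing the stop to the vaccine concerned.

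It does not dispose of the conflict on the day itself. A child febrile at V05 has an active illness, so the self-limiting reading still leaves stop against postpone.

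On follow-up, the reply is that each sentence serves its own list. That fails for the two conditions in both lists. It is fair, however, that safety-only follow-up may be a deliberate choice to spare sick infants study blood draws, so the documents do not show which rule is the wrong one.

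A reader might also infer that 5.2.7.2 contaminates FAS3, because an infant given PCV without M-M-R II or VARIVAX can stay in that set with V06 viral antibody results. That follows from the FAS3 definition and applies to a dose missed for any reason.

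**Conclusion.** The concern holds as two inconsistencies within the protocol. First, an infant febrile at V05 receives conflicting stop and postpone instructions and could lose up to two routine doses; for a mild afebrile infection the conflict concerns VARIVAX only. Second, two follow-up rules apply to immunosuppressive therapy and to severe allergic reaction to a previous dose, with an effect mainly on FAS2 membership when the event precedes V04.

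The size is small. The documents give no rate of febrile illness, infection or the overlapping conditions, so the number affected cannot be derived. It is probably low, because the visit steps say to postpone. No between-arm bias is claimed: the rules are the same for all groups, and all analyses are descriptive. The conclusion rests on the text alone and assumes that sites treat 5.2.7.2 as an operative instruction alongside the visit steps.

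**What to change.** Move M-M-R II item 3 and VARIVAX item 4 to 5.2.7.1, or leave them in 5.2.7.2 and limit them to the day of vaccination until the condition resolves. Keep untreated tuberculosis as a contraindication for as long as it is untreated. Have the sponsor's clinicians state whether a mild infection without fever counts for VARIVAX.

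State a single follow-up rule for conditions that appear in both lists of 5.2.7.2. Whether that rule includes blood sampling is a clinical decision for the sponsor.

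The cost is a few sentences of protocol wording in 5.2.7.1 and 5.2.7.2. Sample size, endpoints and statistical methods do not change.

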5.2.8 Contraindication for Subsequent blood draw

The following is a temporary contraindication to blood draws for toddlers (BL0002 at V02) and for infants (BL0002 at V04 and BL004 at V06):

- 1) Receipt of oral or injectable antibiotic therapy within 72 hours prior blood draw.

Note: If a subject receives oral or injectable antibiotic therapy within 3 days prior to the next blood draw, the Investigator will postpone that blood draw until it has been 3 days since the subject last received oral or injectable antibiotic therapy. Postponement must still be within the timeframe for blood draw. If postponement would result in the sample collection falling outside of this timeframe, the blood sample should be collected without postponement, and it should be documented appropriately (in source documents and CRB) that the sample was taken less than 3 days after stopping antibiotic treatment.

5.2.9 Coronavirus Disease 2019 (COVID-19) Vaccine

Should COVID-19 vaccination campaign be implemented during the course of the study for the pediatric population eligible to participate or participating to the study, applicable country recommendations will be implemented. When possible and unless recommended otherwise, a 2-week interval between any study vaccine dose and the COVID vaccine dose is desirable.

If a COVID-19 vaccine dose is received during one study vaccine solicited reactogenicity period it would not be possible to differentiate systemic reactions between them. Likewise, if the COVID-19 vaccine is received between a study vaccine dose and the collection of blood, it will not be possible (at this point) to rule out an immunogenicity interaction. Therefore, in any of the two situations it is recommended that the subject will be pulled out of the per protocol (PP) population but should continue in the study within the full analysis set (FAS).

The type of COVID-19 vaccine received (including tradename) and the date of its administration(s) should be documented in the concomitant medications CRF.

Wherever possible the site of injection of study vaccines should be in the limb separate from the limb in which COVID-19 vaccine is administered (if it has already been administered). Likewise, and if on the control of the study site, any COVID-19 vaccine scheduled to be received after administration of study vaccines should not be received in the same limb as study vaccines. Where it is not possible to have study vaccines and COVID-19 vaccine administered in separate limbs, a distance of at least 1 inch / 2.5 cm should be maintained between the two administration sites.

5.2.10 Conditions for Withdrawal

Parents / Guardians will be informed that they have the right to withdraw their child from the study at any time. A subject may be withdrawn from the study:

- At the discretion of the Investigator or Sponsor due to safety concerns or significant non-compliance with the protocol (based on the Investigator's judgment), without the subject's permission (withdrawal)
- At the request of the parent / guardian (dropout)

The reason for a withdrawal or dropout should be clearly documented in the source documents and in the CRB.

The Investigator must determine whether voluntary withdrawal is due to safety concerns (in which case, the reason for discontinuation will be noted as "Adverse Event") or for another reason.

Withdrawn subjects will not be replaced.

5.2.11 Lost to Follow-up Procedures

In the case of subjects who fail to return for a follow-up examination, documented reasonable effort (ie, documented telephone calls and certified mail) should be undertaken to locate or recall them, or at least to determine their health status while fully respecting their rights. These efforts should be documented in the source documents.

5.2.12 Classification of Subjects Who Discontinue the Study

For any subject who discontinues the study prior to completion, the most significant reason for early termination will be checked in the CRB. Reasons are listed below from the most significant to the least significant (refer to the CRF completion instructions for additional details and examples):

Adverse Event	To be used when the subject is permanently terminated from the study because of an AE (including an SAE), as defined in Section 9.1.1.1 . This category also applies if the subject experiences a definitive contraindication that is an SAE or AE.
Lost to Follow-up	To be used when the subject cannot be found or contacted in spite of efforts to locate him/her before the date of his/her planned last visit, as outlined in Section 5.2.11 . The certified letter was sent by the Investigator and returned unsigned, and the subject or parent/guardian did not give any other news and did not come to any following visit.
Protocol Deviation	To be used: 
• In case of significant noncompliance with the protocol (eg., deviation of the Inclusion / Exclusion criteria, non-compliance with time windows, blood sampling or vaccination refusal, missed injection/treatment, or error in the vaccine/treatment administration).• If the subject experiences a definitive contraindication that is not an SAE or AE.• The subject or the parent/guardian signed the certified letter sent by the Investigator but did not give any other news and did not come to any following visit.
Withdrawal by Parent / Guardian	To be used: 
• When the subject or parent/guardian indicated unwillingness to continue in the study• When the subject or parent/guardian made the decision to discontinue participation in the study for any personal reason other than an SAE/AE (eg., subject is relocating, inform consent withdrawal, etc.)

5.2.13 Follow-up of Discontinuations

The site should complete all scheduled safety follow-ups and contact any subject who has prematurely terminated the study because of an AE or a protocol deviation.

For subjects where the reason for early termination was lost to follow-up or if the subject withdrew informed consent and specified that they do not want to be contacted again and it is documented in the source document, the site will not attempt to obtain further safety information.

If the subject's status at the end of the study is "Withdrawal by Parent / Guardian", the site will attempt to contact them for the 6-month follow-up except if they specified that they do not want to be contacted again and it is documented in the source document.

5.3 Safety Emergency Call

If, as per the Investigator's judgment, a subject experiences a medical emergency, the Investigator may contact the Sponsor's RMO for advice on how to address any study related medical question or problem. If the RMO is not available, then the Investigator may contact the Call Center—available 24 hours a day, 7 days a week—that will forward all safety emergency calls to the

appropriate primary or back-up Sanofi Pasteur contact, as needed. The toll-free contact information for the Call Center is provided in the Operating Guidelines.

This process does not replace the need to report an SAE. The Investigator is still required to follow the protocol-defined process for reporting SAEs to the GPV Department (please refer to [Section 10](#)).

In case of emergency code-breaking, the Investigator is required to follow the code-breaking procedures described in [Section 6.4](#).

5.4 Modification of the Study and Protocol

Any amendments to this study plan and protocol must be discussed with and approved by the Sponsor. If agreement is reached concerning the need for an amendment, it will be produced in writing by the Sponsor, and the amended version of the protocol will replace the earlier version. All substantial amendments (eg, those that affect the conduct of the study or the safety of subjects) require IEC / IRB approval, and must also be forwarded to regulatory authorities.

An administrative / non-substantial amendment to a protocol is one that modifies some administrative, logistical, or other aspect of the study but does not affect its scientific quality or have an impact on the subjects' safety. The IECs / IRBs will be notified by the Sponsor if such an administrative / non-substantial amendment is made.

The Investigator is responsible for ensuring that changes to an approved study, during the period for which IEC / IRB approval has already been given, are not initiated without IEC / IRB review and approval, except to eliminate apparent immediate hazards to subjects.

